7. Current meditation or intense yoga practice of more than 30 min a week or meditation experience of more than 20 hours in the past 10 years. (Since this pilot is focused on investigating mechanisms, we will limit the sample to participants who are new to mindfulness techniques). (Assessed before the phone-screening using the main study database.)
8. Participants with body weight >230 lbs or BMI > 38 will require additional in-person screening and PI approval, because of potential tight fit in the MRI scanner. (Assessed during the phone-screening.)
9. Participants with vascular disease, such as peripheral vascular disease, varicose veins, or lymphedema, in both lower limbs. (Participants may be included with PI approval, if they have vascular disease only in the right limb, which will not receive cuff-pain stimulation and no signs of disease in the left limb.) (Assessed during the phone-screening.)

10. Based on clinical judgment and safety assessment by the PI, the participant is inappropriate for fMRI or unable to complete experiments. (Assessed only if after the phone-screening and other interactions with the patient, the study personnel has doubts about the patients' ability to participate in this additional study.)

C.1.c.3. Patient Participant HEART Pilot Additional Inclusion Criteria:

1. Participant must be currently enrolled in, or have completed, the MINDFUL-PC study.
2. Participant must have access to a smartphone that is compatible with the activity tracker application.
3. Participant must be willing to use the smartphone application and/or wear a wristband activity tracker every day for activity monitoring periods of the HEART study and be willing to take pictures of their food and drink intake.
4. Participant must be able to fill out the study questionnaires daily on a computer or compatible mobile device.

Screening will be conducted by study staff and research assistants. Decisions on the inclusion/exclusion will be made by the study staff under the supervision of the neuroimaging postdoctoral fellow and Principal Investigator in cases where no additional clarifications are needed. In cases where MRI safety needs further assessments, the postdoctoral fellow or imaging consultants at the Martinos Center for Biomedical Engineering will coordinate the assessment with the MRI physics staff at the Martinos Center, and will decide on inclusion or exclusion of the participant.

C.2. Recruitment:

C.2.a. PCP Recruitment:

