During the scheduling phone call for the mindfulness group only, patients are asked about their interest in the optional fMRI pilot study. We will then screen interested mindfulness group participants verbally, using a phone screening interview based on the Martinos Center MRI Patient Screening form and the Edinburgh Handedness Inventory (see phone script Pt Protocol - Randomization Status Phone Call). We will assess if participants fulfill all criteria related to the fMRI study. Participants will be given the opportunity to ask questions they have regarding the study, the flyer, the information sheet or other aspects regarding the fMRI. Some screening questions represent an immediate exclusion from the study (see phone screening script), other items represent potential risks, and require further clarification. In this case, the responsible Operations Manager and Chief MRI Technologist at the Martinos Center for Biomedical Engineering will be contacted by the neuroimaging post-doctoral fellow, with the necessary information to decide the safety for fMRI scanning for a patient with a certain condition. In case the responsible Operations Manager cannot confirm MRI safety, the patient will be excluded from the fMRI study. Participants will also be asked if they have used any illicit drugs in the past 30 days, and any drug use could result in exclusion from the study based on the clinical judgment of the PI. If a patient fulfills all eligibility criteria, we will then schedule an fMRI measurement scan session. If the patient needs additional time to decide about participating in this study or if we have to make additional enquiries based on the MRI eligibility screening, we will arrange a

follow-up phone call with the patient (within 1-2 days of the group-scheduling phone call), to decide on study participation and potentially schedule the fMRI measurement.

C.3.d.4. Overview of Patient Visits in HEART pilot study (see Table 4 in APPENDIX)

HEART Pilot Study Informed Consent Session:

Concurrent Cohort:

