We will phone screen interested MINDFUL-PC group participants for fMRI eligibility, using an fMRI screening phone interview, including items from the **Edinburgh Handedness Inventory** (EHI) [61]. This is a 10-item standard measurement scale used to assess the dominance of a person's right or left hand in everyday activities. Left-handers have less lateralization of brain function and can confound fMRI studies.

Further eligibility questions are based on the Martinos Center Patient Screening Form. Questions are related to metal implants, pacemakers, aneurism clips and other implants and stimulators that might be unsafe for scanning. The form will also ask about pregnancy and breastfeeding, past severe head trauma, claustrophobia or other conditions that might exclude them from participating in the fMRI study. We will also screen for vascular disease in the legs, such as

peripheral vascular disease, lymphedema, and varicose veins, in order to exclude those for whom the cuff pain task may not be safe. The fMRI screening form will be assessed during the phone call. The duration of the phone screening is 10 minutes total. The Martinos Center Screening Form will be acquired again before each scan session, and this will take 3-5 minutes.

We will conduct **saliva toxicology** for alcohol and illicit drugs at the Martinos Center before each MRI session. Duration 5 min.

In case a woman is not on contraception and has doubts about current pregnancy status, she will be given the option to conduct a **urine pregnancy screen** before each MRI session. Duration 5 min.

We will conduct fMRI neuroimaging before and after the MTPC group. Each session will also include autonomic monitoring of heart rate, breathing rate, and skin conductance. Duration 90 min.

fMRI questionnaire: Patients who undergo fMRI neuroimaging will be asked to complete a set of fMRI questions that ask about fatigue, concentration, and presence of pain before and after the pain cuff task (Duration: 5min).

C.3.g. Instructor Experience, Fidelity, and Supervision:

We have developed a detailed plan for training, monitoring and supervising staff that will deliver the intensive behavioral training interventions, as well as for maintaining adherence to protocol.

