1. MRI

The MRI system used in this study has been approved by the FDA and will be operated within the parameters reviewed and accepted by the FDA. MRI is not associated with any known

adverse effects except in people with non-MR-compatible features such as certain kinds of implants, tattoos, jewelry or other devices. Subjects will be excluded from this study if they have any MRI contraindication. The MR Safety Form will be administered prior to every MRI scan to confirm eligibility and subjects will be checked with a metal detector prior to entering the scanner. Some patients find it unpleasant or feel anxious when confined in the enclosed space of the scanner. Subjects will be able to converse with a staff member via a microphone and speaker system, and can request that the scan be stopped at any time for any reason. Subjects will be required to wear earplugs and have additional padding around their ears to prevent discomfort due to scanner noise (<https://www.nmr.mgh.harvard.edu/martinos/userInfo/safety/index.php>).

2. Pain task

In some cases, cuff pain stimulation can result in mild bruising associated with inflation of the cuff. The pressure from this cuff is controlled to be within a safe and tolerable range. If participants feel distress while wearing the cuff, the procedure will be stopped. Patients will be assessed for peripheral vascular disease, varicosities, and lymphedema prior to application of cuff pain to prevent the possibility of worsening of symptoms.

3. Emotional Go/NoGo task

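### fMRI pilot exclusion item 9 bars leg vascular disease only when it is in both legs, so as written it does not exclude disease confined to the cuffed left leg

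*Combined protocol and SAP*

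**What the plan says.** The criterion is item 9 of C.1.c.2, assessed at the phone screen. It excludes "Participants with vascular disease, such as peripheral vascular disease, varicose veins, or lymphedema, in both lower limbs". A bracket follows: with the principal investigator's approval, a participant may be included if the disease is "only in the right limb, which will not receive cuff-pain stimulation and no signs of disease in the left limb".

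Four other places bear on the point.

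- **C.1.c.2, item 10** allows exclusion on the investigator's clinical and safety judgment, but it is "Assessed only if after the phone-screening and other interactions with the patient, the study personnel has doubts" about the patient's ability to take part.
- **The screening paragraph after C.1.c.3** covers cases that need no further clarification: "Decisions on the inclusion/exclusion will be made by the study staff under the supervision of the neuroimaging postdoctoral fellow and Principal Investigator". **The Group Scheduling Phone Call in C.3.d.3** says some answers exclude at once, while "other items represent potential risks, and require further clarification".
- **C.3.f.14** says "We will also screen for vascular disease in the legs", and gives the purpose: "in order to exclude those for whom the cuff pain task may not be safe".
- **D.2.d.2 (Pain task)** says patients will be "assessed for peripheral vascular disease, varicosities, and lymphedema prior to application of cuff pain", so that symptoms are not made worse.

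The description of the pre-treatment fMRI session says the cuff goes on the calf but does not name a side.

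**The concern.** The two halves of item 9 do not describe the same rule. The lead sentence, on its face, concerns bilateral disease only. The bracket grants an exception for right-only disease, which the lead sentence never excluded. Left-only disease is in neither half, although the left leg is the one that is compressed.

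The literal result is stricter for the uncuffed leg than for the cuffed one, which reverses the item's own rationale. Item 9 is an operative safety criterion applied by study staff, and it is the only place in the protocol that says which leg matters. Staff should not have to work out from a waiver that disease in the cuffed leg disqualifies a patient. What is at stake is participant safety in the pain task, not any estimate or test.

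**Working it through.** No figure in the plan needs reproducing. The check is a comparison of texts.

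**Step 1: which leg is cuffed.** The bracket says the right leg gets no cuff and requires the left to be free of disease. The cuffed leg is therefore the left.

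**Step 2: list the disease patterns.** The rule implied by the bracket treats right-only disease as something that needs a waiver and requires a clear left leg. That rule is set against the literal lead sentence, and against the lead sentence with *either lower limb* in place of *both lower limbs* and the waiver kept.

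| Disease pattern | Rule implied by the bracket | Lead sentence as written | *Either* plus existing waiver |
|---|---|---|---|
| Left only (cuffed leg) | Excluded | Not excluded | Excluded |
| Right only (uncuffed leg) | Excluded unless approved | Not excluded | Excluded unless approved |
| Both legs | Excluded | Excluded | Excluded |
| Agreement with implied rule | – | 1 of 3 | 3 of 3 |

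The two mismatches differ in weight. For right-only disease the bracket is simply more cautious than the lead sentence. For left-only disease the cuffed leg is left uncovered. So one pattern of the three carries the safety question.

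**Step 3: try other readings.** If the bracket is a free-standing approval requirement for right-only disease, left-only disease is still not covered by item 9. If *both* is read loosely to mean *either*, the item works, but that concedes the word is wrong.

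**Step 4: see whether other text supplies the rule.** C.3.f.14 and D.2.d.2 refer to the same three conditions with no bilateral limit, which supports the intended reading. Neither says which leg matters. Item 10 depends on staff already having doubts. The phone script is not among the documents, so whether it asks about each leg separately cannot be checked.

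**Step 5: size.** C.2.c caps the pilot at 30 patients and C.2.b plans 290 in the intervention arm, so the pilot is at most 30 / 290 = 10.3% of that arm. The protocol gives no prevalence of left-only disease, so the number affected cannot be estimated.

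**The case against.** The strongest reply is that the bracket is part of the criterion. It requires a left leg with no signs of disease, so a left-only patient fails the stated condition unless the first sentence is read alone. C.3.f.14 already aims to exclude anyone for whom the cuff may be unsafe, and D.2.d.2 adds a check tied to the cuff itself. An instruction of that kind need not name a limb. Item 8, directly above, uses investigator approval as a requirement in its own right, so the bracket in item 9 might be meant the same way. Without the phone script, no failure in practice is shown. Harm is also bounded: D.2.d.2 names mild bruising, keeps cuff pressure within a tolerable range, and stops the procedure if the participant is distressed.

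Much of this stands. The intent is clear when the item is read whole, the other checks would probably stop a left-only patient, and no operational gap has been demonstrated. These points limit the severity. They do not repair the sentence. The item 8 comparison is weak, because item 8 imposes a requirement whereas item 9 grants permission, and Step 3 shows that this reading leaves left-only disease uncovered anyway.

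**Conclusion.** The concern holds, as a minor wording fault in a safety exclusion criterion. Item 9 as written does not exclude disease confined to the leg that receives the cuff.

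The conclusion rests on two things the text supports: the left leg is the cuffed one, and the bracket is a waiver from a default exclusion. It does not assume that any patient was, or would be, wrongly admitted. The exposure is confined to the optional imaging pilot. Main-trial endpoints, analyses and sample size are unaffected.

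**What to change.** In C.1.c.2 item 9, replace *both lower limbs* with *either lower limb*, and keep the approval route for right-only disease with a clear left leg. Rewording to *left or both* would be a poorer choice: right-only disease would then not be excluded at all, and the waiver would be redundant.

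Two optional additions would help: name the left calf in the pre-treatment fMRI session description, and confirm that the phone-screen question asks about each leg separately.

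The cost is one word and a plural. The change adds no procedure or visit and should have a negligible effect on pilot recruitment.

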Within this naturalistic implementation project, we will conduct a randomized controlled trial of CHA patients with a PCP referral. Patients will be randomized using a stratification algorithm to receive either MTPC training or one 60-min introduction to mindfulness session. This randomization will be based on the level of mindfulness training of the patient’s primary care provider (Group 1 vs. Group 2 and 3). Those patients who are randomized to receive MTPC training (MTPC Group) will be instructed by behavioral health specialists who are trained as MTPC Group Leaders, as described later in section C.4.a. of the protocol. The MTPC group is a group psychotherapy intervention held within a primary care health center on 8 consecutive weeks with 10-12 enrolled patients with 2 hour-long sessions, including a 7-hr day of silent practice. As the level of desire to participate in mindfulness training may be a confounding factor, we will use a 60-min introduction to mindfulness group as a control in order to eliminate bias related to expectation and selection that could otherwise influence measures of treatment effect. In contrast, those patients who are randomized to receive only the 60-min introduction to mindfulness (Control Group) will be given preference to enroll in MTPC after the study’s completion. Both groups of patients will complete surveys at the induction of the study, again after patient study week 8, and at study week 26 (see Figure 1b). Patients will complete an interview with a research coordinator to assess their maintenance of their action plan goal at week 26.

Figure 1b. Study flow schema for Patient participants

In this RCT, we will also conduct an optional experimental fMRI pilot study. This study will include a pre/post within-subjects design with 90 minutes of neuroimaging before and after completion of the MTPC group. Each scanning session will begin with setting up the equipment for autonomic monitoring (i.e., respiratory belts, finger plethysmograph, finger sensors for skin

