This study will not be blinded; however, upon referral, all patients will receive a screening from the primary care behavioral health care provider, complete an informed consent, complete a set of pre-treatment baseline surveys and then will be informed that they will be given a random

number and placed on the waiting list for upcoming groups. They will be told about capacity restrictions, that there will be two groups consisting of different group lengths, and that if they would like to do more groups after completion of the program, they will be notified about groups that become available sometime in the next year or two.

C.3.d. Study Visits:

In this section, the flow of study visits will be described for both PCPs and Patient participants.

PCP Study Visits have been completed as of February 10, 2017. No additional PCP study visits will take place after this date.

C.3.d.1. Overview of PCP Study Visits (SEE TABLE 2 IN APPENDIX A):

Phone Screen Visit (PCP Group 1a or Group 1b):

PCPs who express interest in the MBSR program or the weekend 18-hr mindfulness retreat will be screened by phone or email by the study Research Coordinator who will register PCP participants for the study at one of the Patient-Centered Medical Homes. At the time of registration, the PI, Research Coordinator or a research assistant will conduct a brief screening interview to determine the PCP's eligibility for the study. This will take 10 minutes by phone or email.

Phone Screen Visit ([PCP Group 2 and 3]):

PCPs who express interest in referring patients to mindfulness groups will be asked to fill out an eligibility questionnaire on paper or through a secure REDCap link. Eligible PCPs will be given the opportunity to continue on to the informed consent session.

Informed Consent Visit (PCP Study week 1 [Group 1a, s, or Group 2 and 3] or Week 10 [Group 1b]):

PCP participants will be provided with written descriptions in English of the research study procedures, timeline and participant commitments electronically through a secure REDCap link for review prior to enrollment. PCPs will be given an opportunity to email and/or call the study staff for answers to any questions about the consent document and they will be asked to complete a consent quiz to ensure understanding of the most crucial points.

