In order to be eligible to participate in the MINDFUL-PC study, all patients must have a CHA PCP, and a referral from their CHA PCP or a licensed CHA mental health clinician. .

In order to be eligible to participate in the MINDFUL-PC study, all patients must have a MINDFUL-PC Patient Screening Form completed by a behavioral health care provider upon performing a behavioral health evaluation. Patients must fill out a Patient Eligibility Questionnaire electronically via an e-mail link to a secure REDCap form or by voice over phone. This questionnaire will be reviewed by the MINDFUL-PC PI or Center for Mindfulness and Compassion Medical Director, who will then assess the eligibility of the patient and schedule a 1-hour behavioral health evaluation, if appropriate. The behavioral health clinician will conduct a behavioral health evaluation to determine the patient’s eligibility for the study and to enroll patients into the program. Data from the screening interview, MINDFUL-PC Patient Screening Form, and Patient Eligibility Questionnaire will be entered into a secure REDCap form.

Since the research study is overlaid on an implementation pilot program, we will rely on the assessment of the referring mental health clinician (either a masters or doctoral level clinician) to identify patient diagnoses and the presence of any severe mental illness. The Research Coordinator or other IRB-approved study staff with non-clinical training, but background in

psychology will be reviewing diagnoses on the submitted screening forms. Any diagnoses that suggest major mental illness will be reviewed with the PI daily. The PI is a board-certified psychiatrist and will decide if a patient with mental illness will be included and excluded from the study. If the decision is unclear from the referral documentation, then the principal investigator will contact the screening behavioral care provider to discuss the patient's appropriateness for the study. If the patient passes the screening interview, he or she will be offered to be scheduled to attend the Mindfulness Orientation Session.

Mindfulness Orientation Session (Prior to Randomization; To be scheduled prior to PT Study Week 1):

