Patients who have consented to participate in the study and have completed the pre-treatment survey session will be invited to stay for the 60-minute mindfulness orientation session. During this session, interested patients will meet for one visit with a behavioral care provider in groups of up to 30 participants. This group will be held within a clinical space at each participating CHA primary care health center. It will be one hour in length and the behavioral care provider will offer a list of mindfulness resources available in the community. Patients will be reminded that, after this session, they will be randomly assigned to either the 8-week or referral to community resources and electronic resources and placed on a 6-month waiting list. Details about this intervention can be found in section C.3.e.3.

Scheduling Phone Call:

Once an eligible individual has demonstrated an understanding of the study procedures and potential risks of participating, provided written informed consent, completed pre-treatment assessments on REDCap, and attended the MTPC orientation session, then he or she will be placed onto the waitlist for randomization for the respective health center and assigned a randomization ID by health center. This ID will be entered into a randomized algorithm with stratification, which will be used to allot the participant to a study group. The Research Coordinator or another approved member of the research personnel will contact the patient by phone to schedule him/her for the specified study group, and a scheduling email will be sent. Patient participants will be assigned either to an 8-week MTPC group or to a 6-month waiting list for the MTPC group, and will be informed of their placement during the phone call. Patients will also be encouraged at this time to ask any questions they might have.

If a participant cannot attend the assigned group, he or she will have to wait to be rescheduled for at least 6 months from the completion of his/her pre-treatment assessments.

Biweekly Engagement Phone Call (PT Study Week 1-8):

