Mixed Effects Modeling to evaluate for main effects of PCP mindfulness training and main effects of Patient training level (1 hour vs. 8 week) for each survey, as well as the interaction effect with relevant covariates.

3. *Health Outcomes Hypotheses*: We hypothesize reductions in depression, anxiety and stress as a main effect of MTPC. Finally, we hypothesize reductions in use of medications prescribed for symptom reduction (benzodiazepines, opioids, etc.), overall improvement in markers of health maintenance and chronic illness management (i.e. PQRS data). We hypothesize the highest levels of initiation and maintenance of self-management action plans among MTPC group with Mindfulness-trained providers.

Mixed Effects Modeling to evaluate for main effects of PCP mindfulness training, main effects of Patient training level (1 hour vs. 8 week) for each outcome, as well as the interaction effect with relevant covariates.

4. *Provider Resilience Hypothesis*: We hypothesize greater workplace well-being, reduced experience of burnout, and increased resiliency among providers as a main effect of provider MBSR + Mindful Communication training.

We will use Mixed Effects Modeling to evaluate for main effects of PCP mindfulness training and time for each survey and the interaction of the two.

5. *Medical Regimen Adherence Hypotheses*: We hypothesize a main effect of MTPC group status on levels of initiation and maintenance of medical regimen health behavior change, as measured by the APIS-5 self-report score. The highest levels will be demonstrated among the MTPC group participants with mindfulness-trained providers. We hypothesize that total formal mindfulness practice, post-study total mindfulness score, baseline mindful non-judgment score, and self-compassion will be associated with successful initiation and maintenance of action plans. Action plan initiation will be validated by increases in step count, and increases in number of active periods, changes in sleep, changes in mindfulness practice, and changes in nutritional habits.

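### The 60-minute session said to control for expectation is given to both arms before randomisation, so it cannot balance expectation that arises once patients know their allocation

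*Combined protocol and SAP*

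**What the plan says.** **Design sections.** C.3.a says patients are randomised "to receive either MTPC training or one 60-min introduction to mindfulness session" and gives the reason for that control: "we will use a 60-min introduction to mindfulness group as a control in order to eliminate bias related to expectation and selection". C.3.c repeats the allocation, at 2:1, and states that the study is not blinded.

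**Visit sections.** C.3.d.2 heads the session "Mindfulness Orientation Session (Prior to Randomization; To be scheduled prior to PT Study Week 1". Patients who have consented and completed the baseline surveys "will be invited to stay for the 60-minute mindfulness orientation session". At that session, "Patients will be reminded that, after this session, they will be randomly assigned to either the 8-week or referral to community resources" with a 6-month wait. Under Scheduling Phone Call, the patient is listed for allocation only once he or she has, among other steps, "attended the MTPC orientation session, then he or she will be placed onto the waitlist for randomization". Allocation is then to an 8-week MTPC group or a 6-month waiting list, and the patient is told which by phone.

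**Schedule.** Table 3 in Appendix A has one 60-minute group orientation, before Week 1, with no mark restricting it to one arm. No second 60-minute session appears anywhere in the protocol.

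**Analysis sections.** C.5.b names the factor as "main effects of Patient training level (1 hour vs. 8 week". C.5.c and D.4.c call the control patients orientation only. The goal statement in D.4.c names the comparator as referral to community resources.

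**The concern.** A session can act as a control condition only if it is what the control arm receives in place of the treatment. Here it precedes allocation and is shared, so it works as a common run-in. Expectation bias in an open trial comes mainly from knowing one's arm: hope in those who start the course, disappointment in those told to wait. A run-in held before that knowledge exists cannot even it out.

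The session may even sharpen the contrast. According to C.3.e.3 it is meant to build commitment to daily home practice, go through the schedule of the coming course and introduce its leaders. One third of those randomised are then told to wait.

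What is at stake is interpretation. The goal in D.4.c concerns anxiety, stress and depression, measured with DASS-21, PROMIS and PSS. The outcome used for the sample size, action plan initiation, is measured with APIS-5. All are self-reports by patients who know their arm. A report that took its description of the control from C.3.a would credit the design with a protection it does not have.

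**Working it through.** **1. What each arm receives**

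| Element | MTPC arm | Control arm | Source |
|---|---|---|---|
| 60-minute orientation, before randomisation | yes | yes | C.3.d.2, Table 3 |
| Community resource list, given at orientation | yes | yes | C.3.d.2, C.3.e.3 |
| Told allocation by phone | yes | yes | C.3.d.2 |
| Biweekly calls, weekly diaries, action plan worksheet and video | yes | yes | C.3.d.2, C.3.f.9 |
| MTPC during the study | yes | no; 6-month wait | C.3.d.2 |

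MTPC hours: 8 sessions × 2 h + 7 h = 23 h, the total given in C.3.d.2. Total training is therefore 1 + 23 = 24 h against 1 h. The randomised difference is 23 h of MTPC, and for the 60-minute session it is 0.

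**2. Which part of the claim survives**

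- *Selection.* Both arms are drawn from patients who reached the same point before allocation, and allocation is random. This part holds.
- *Expectation before allocation.* Both arms have had the same information and exposure. This part is reasonable.
- *Expectation after allocation.* There is no blinding, placement is disclosed, and no element is given to controls in place of MTPC. Calls, diaries and worksheets go to both arms, so they do not act as a control-specific attention condition. This part fails.

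**3. The plan's own figure**

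Inputs from C.5.c: 290 and 144 patients, rates 0.68 and 0.54, two-sided 0.05.

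- Pooled rate = (144 × 0.54 + 290 × 0.68)/434 = 0.6335
- SE under the null = √[0.6335 × 0.3665 × (1/290 + 1/144)] = 0.0491
- SE under the alternative = √[0.54 × 0.46/144 + 0.68 × 0.32/290] = 0.0498
- Power = Φ[(0.14 − 1.96 × 0.0491)/0.0498] = 81.0%

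The stated 80% reproduces, so the sample-size arithmetic is not at issue.

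**4. Illustration under assumed bias**

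The documents give no size for expectation bias, so every shift below is an assumption. Suppose MTPC has no effect, both true initiation rates are 0.54, and knowing one's arm raises reported initiation in the MTPC arm only. The same formula gives the chance of a significant result:

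| Assumed shift (points) | 0 | 2 | 5 | 10 | 14 |
|---|---|---|---|---|---|
| Chance of p < 0.05 | 5.0% | 6.8% | 16.9% | 51.9% | 81.0% |

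For a continuous scale, SE = √(1/290 + 1/144) = 0.102 SD, and the difference detectable with 80% power is (1.960 + 0.842) × 0.102 = 0.29 SD. Assumed shifts of 0.1, 0.2 and 0.3 SD would be significant 17%, 50% and 84% of the time. These are crude two-sample values without the covariates or mixed models of C.5.b.

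**The case against.** The strongest reply is that most of the design is sound and the fault lies in one sentence. Much of that stands.

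- *The claim covers selection as well as expectation.* Correct, and the selection part holds. A reader might infer that the stated protection is absent altogether. The documents do not support that.
- *Controls are not simply left waiting.* Correct. They have the referral, biweekly calls, diaries, action plan materials and preference for MTPC afterwards. Calling the comparator a bare waiting list would be inaccurate. These elements are essentially shared, however, so they do not offset expectation specific to one arm.
- *The factor label can mean total dose.* This is a fair reading, since C.3.a says controls receive only the introduction. A reader might infer that the analysis is misspecified. It is not: the coding separates the randomised arms, and a new label changes no model, estimate or test.
- *Patients are told about the wait.* A reader might take "that there will be two groups consisting of different group lengths" in C.3.c to mean that the waiting list is hidden until later. The same paragraph mentions placement on a waiting list, capacity limits and notice of later groups. C.3.d.2 is more explicit, but the two differ in emphasis and are not opposed.
- *The true comparator is named elsewhere.* D.4.c does name referral. This limits the risk of misreporting, but leaves sections that describe different control conditions.
- *Attendance by all 434 is not certain.* The eligibility sentence in C.3.c lists screening, consent and baseline surveys but not attendance. C.3.d.2 both invites patients to the session and makes attendance a condition for allocation. That inconsistency needs settling.
- *The bias figures would fit any unblinded trial of this size.* True. They show what unmeasured expectation could do and do not estimate what it did here.

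**Conclusion.** The concern holds for expectation after allocation, and only for that. The plan attributes to the 60-minute session a protection that its own visit flow rules out. The session is shared and precedes randomisation, so the randomised contrast is 23 hours of MTPC against referral and a 6-month wait, with calls, diaries and action plan materials common to both arms.

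The randomised comparison remains valid as a comparison of those two strategies, and a waiting-list comparator is a legitimate choice. What cannot be concluded is that a difference in DASS-21, PROMIS, PSS or APIS-5 is free of expectation effects, or that MTPC outperformed a separately delivered one-hour control.

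A reader might go further and read 17% or 52% as this trial's false-positive rate. The documents do not support that: those values rest on assumed shifts of 5 and 10 points. The size of any bias here is unknown.

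The verdict assumes that the visit flow in C.3.d.2 and Table 3 describes what is done, and that no further 60-minute session is held for controls after allocation.

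**What to change.** 1. **C.3.a and C.3.c.** Describe the comparator as community-resource referral and a 6-month waiting list, with the biweekly calls, diaries and action plan materials common to both arms, after a 60-minute orientation given before randomisation. Withdraw the claim to eliminate expectation bias. Protection against selection may stay, credited to randomisation.
2. **C.5.b.** State that the randomised contrast is MTPC against waiting list with referral, both after orientation, and that conclusions on self-reported outcomes (DASS-21, PROMIS, PSS, APIS-5) are not controlled for expectation. Relabel the training-level factor to match. This is for clarity and alters no model.
3. **Consistency.** Reconcile C.3.c, which does not list attendance at orientation, with C.3.d.2, which requires it before randomisation. Align the two sections on what patients are told before allocation.

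An expectation question added to the calls is not proposed as a remedy. Enrolment was planned from September 2015 (C.4.b) and the latest listed version is dated June 2018, so the question would miss patients already enrolled. An answer given after allocation also could not correct the bias. If a bias calculation is reported, label it as an illustration under assumed shifts.

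The cost is an amendment to wording, with no change to sample size, visits or models. The downside is a more modest claim.
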